4.2 Safety Variables

Safety is monitored in this study by collection of adverse events, vital signs, electrocardiography, and clinical laboratory measures. It is noted that all untoward events or experiences are reported as adverse events regardless of whether they are identified by clinical observation, subject reporting, physical examination, clinical laboratory test result, electrocardiography, or any other examination or test. It is noted that listings are reviewed by medically qualified individuals of vital signs, laboratory data, electrocardiograms (ECG), and all safety data from all other sources to ensure that safety signals are identified and reported in the analysis of the safety data from this study.

4.2.1 Treatment-emergent Adverse Events

Adverse events will be coded using Medical Dictionary for Regulatory Activities (MedDRA) Version 16.0 or above. Adverse event coding will be done to the lowest level term (LLT). Adverse events will be summarized by System Organ Class (SOC) and preferred terms (PT).

Definitions:

- A treatment-emergent adverse event (TEAE) is an event that is observed or reported after administration of study medication that was not present prior to study medication administration or an event that represents the exacerbation of a pre-existing event.

- An adverse withdrawal is a subject who withdrew from the study due to an adverse event.
- A serious adverse event (SAE) is an AE that is classified as serious according to the criteria specified in the study protocol.

Safety and tolerability variables based on adverse events include the following:

- Proportions of subjects with TEAEs by Preferred Term and decreasing frequency of AEs
- Proportions of subjects with TEAEs by System Organ Class and Preferred Term
- Proportions of subjects with related TEAEs
- Proportions of subjects with severe TEAEs
- Proportions of subjects with treatment-emergent SAEs.
- Subjects with TEAEs that result in study termination.

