9.3 SAFETY ANALYSIS

A treatment-emergent adverse event (TEAE) is defined as an AE that was not present at baseline, or an exacerbation of a pre-existing AE. For laboratory data, a treatment-emergent abnormal laboratory value (TEAV) represents an abnormal value that was normal at baseline.

Safety variables of analysis include the following:

- Proportions of patients with any TEAEs
- Proportions of patients with serious TEAEs
- Proportions of patients with severe TEAE
- Proportions of patients with TEAEs leading to study drug discontinuation
- Proportions of patients with TEAEs leading to study withdrawal
- Proportions of patients with drug-related TEAEs
- Proportions of patients with TEAVs
- Proportions of patients meeting DILI criteria
- Proportions of patients meeting ICH E14 criteria for threshold values or threshold changes
- Mean changes from baseline in vital signs
- Mean changes from baseline in clinical laboratory measures
- Mean change from baseline in measures from electrocardiography

Continuous data will be summarized by treatment group using descriptive statistics (number, mean, median, standard deviation, first and third quartiles, minimum, and maximum). Categorical data will be summarized by treatment group using frequency tables (frequencies and percentages).

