1.5 Study Design

This is an open-label extension study in patients with mild Alzheimer's disease who have successfully completed participation in the azeliragon Phase 3 TTP488-301 (STEADFAST) trial. Patients may receive azeliragon 5 mg/day for up to 2 years.

Participants were required to continue to be on SoC of a stable background acetylcholinesterase inhibitor therapy and / or memantine and continue the therapy for the duration of the trial, unless the investigator judges that the dose needs to be reduced or stopped due to a safety and/or tolerability reason.

Subjects were expected to participate in approximately 9 outpatient visits including baseline which is the same visit at the Month 18 visit in the TTP488-301 study.

Protocol TTP488-301 included two studies with a common infrastructure (A-study and B-study). Participants from either study are allowed to roll over into this open-label extension study.

A-study is conducted at multiple sites in the US and Canada. B-study is conducted at multiple sites in the US, Canada, Ireland, UK, South Africa, New Zealand, and Australia.

This study was terminated prematurely before participation outside of the US and Canada began; therefore, this study is conducted at multiple sites in the US and Canada.

The overall structure of the study includes the following periods:

Baseline Study Period: (Month 18 visit of TTP488-301): At the Month 18 visit of TTP488-301, subjects who met eligibility requirements were offered enrollment into this open-label extension study. Subjects had baseline assessments for efficacy and safety measures, including PK assessments.

Treatment Period: (Day 1 (Month 18 visit of TTP488-301) — Month 24): Subjects were treated with open-label azeliragon 5 mg QD. Efficacy and safety measures were taken. Blood samples were taken and subjects have assessments for safety and PK.

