1.7 Early Stopping, Data Monitoring, and Interim Analysis

There is no interim analysis in this study, except for medical and safety monitoring by the independent data monitoring committee (IDMC). This study has no plan for early stopping.

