1.9 Modifications from the Statistical Section of the Protocol

There are no modifications from the Statistical Section of the Protocol.

2 Statistical Hypotheses

There are no formal statistical hypotheses for this open-label study.

3 Populations of Analysis

In accordance with guidance from the International Conference of Harmonization of Technical Requirements for Registration of Pharmaceuticals for Human Use (ICH) guideline ICH E9 Statistical Principles for Clinical Trials (1998), the following population of analysis will be used for all statistical analysis:

- The full analysis set (FAS) includes all randomized subjects who receive any study medication and have at least one post-Baseline assessment.
- The per protocol set (PPS) includes all subjects in the FAS, except for those who are excluded because of major protocol violations, where a major protocol violation is one that may affect the interpretation of study results (e.g., taking less than 50% of prescribed study medication during participation).

Final determinations of the PPS will be made at the final data review meeting (DRM) held in accordance with ICH E9 prior to the lock data.

- The safety set (SAF) includes all patients who received at least one dose of study medication. The SAF is used for all safety analyses.

The FAS is used for efficacy analysis; the SAF will be used for safety analyses.

It is noted that if the FAS and PPS do not differ by more than 15% in numbers of individuals, analysis may be limited to FAS.

4 Variables of Analysis

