5.3 Analysis of Safety Data

5.3.1 Adverse Events

Adverse events reported in this study will be coded using MedDRA®, Version 16.0, or later. Coding will be to the lowest level terms (LLT). The verbatim text, the preferred term, and the primary SOC will be listed in subject listings. Summaries that include frequencies and proportions of patients reporting AEs will include the preferred terms and the SOCs. Summaries will include TEAEs by severity and by relationship to study medication.

Adverse event summaries will be constructed displaying AEs in decreasing order of total frequency according to the numbers of subjects reporting the AE (not the number of reports).

- Number (percent) of subjects reporting TEAE by treatment and overall in accordance with variables listed in Section 4.2.1.

Supportive listings will be constructed that includes the subject identification, the treatment group (based on randomization from TTP488-301 and the pooled group of enrollees from TTP488-303), TEAEs, MedDRA terms, seriousness, severity, causality, elapsed time to onset, duration, and outcome.

Methodology for AESIs will follow the same methodology for TEAEs.

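### Adverse events are planned only as counts or crude percentages of dosed subjects, with no exposure or patient-year summary, in a study of up to 2 years that was terminated early

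*SAP*

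**What the plan says.** Protocol 2.1 and SAP 1.1 give one primary objective, the collection of long-term safety and tolerability data. Adverse events are the first component of the primary endpoint (protocol 2.2).

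- **Protocol 9.3** opens its list with "Proportions of patients with any TEAEs". The other adverse-event items (serious, severe, drug-related, leading to drug discontinuation or study withdrawal) are also proportions.
- **SAP 4.2.1** begins with "Proportions of subjects with TEAEs by Preferred Term and decreasing frequency of AEs". Four further items are proportions, and one concerns subjects whose events ended participation.
- **SAP 5.3.1** sets the method: "Number (percent) of subjects reporting TEAE by treatment and overall in accordance with variables listed in Section 4.2.1". Events are ranked by subjects affected, not by number of reports. Adverse events of special interest (AESIs) are handled in the same way.
- **SAP 3** sets the denominator: "The safety set (SAF) includes all patients who received at least one dose of study medication".
- **SAP 1.5** allows up to 2 years of treatment and also states: "This study was terminated prematurely before participation outside of the US and Canada began".

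The items closest to exposure are listings. SAP 9 plans a dosing listing and a listing of withdrawals with study day. SAP 5.3.1 plans an adverse-event listing that includes time to onset and event duration. By-visit safety summaries also report the number of subjects available (SAP 5).

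**The concern.** A percentage of dosed subjects depends both on how often events occur and on how long subjects were observed. With a fixed, completed follow-up the second element is known. Here it probably is not. Entry was tied to each subject's own completion of TTP488-301 (protocol 4.1), so start dates are staggered, and the study then stopped early. Truncated and unequal follow-up is a fair inference, although the documents give neither a termination date nor the achieved exposure.

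A reader of the stand-alone report would therefore see that some percentage of subjects had a serious event, with no table showing how many patient-years produced it. Such a figure cannot be read as 2-year risk or set beside a figure of fixed duration. The gap matters most for uncommon serious events. A result of no subjects affected gives the same percentage whatever the follow-up, while the rate it excludes depends on the patient-years accrued.

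**Working it through.** **Step 1: text check.** Protocol 9.2 to 9.5 and SAP 3, 4.2, 4.4, 5, 5.2, 5.3.1, 5.5, 6 and 9 were read for any treatment-duration summary, patient-year total, incidence rate or time-to-event summary of adverse events. None is specified. The plan states no event rate, sample size or exposure for this study, so there is no figure to reproduce. All the numbers below rest on assumed inputs and show only how the measure behaves.

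**Step 2: one percentage, different rates.** Assume a crude 20%, equal follow-up of m months for everyone, and constant hazard. Then rate = −ln(1 − 0.20) / (m/12), with −ln(0.80) = 0.2231.

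| m (months) | First events per 100 patient-years |
|---|---|
| 6 | 44.6 |
| 12 | 22.3 |
| 18 | 14.9 |
| 24 | 11.2 |

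**Step 3: zero events.** Assume N = 200 dosed subjects, none with the event.

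- Two-sided 95% upper limit for the proportion: 1 − 0.025^(1/200) = 1.83%, whatever the follow-up.
- Upper limit for the rate: −ln(0.025) / (N × m/12) = 3.689 / (200 × m/12). For mean follow-up of 6, 12, 18 and 24 months this is 3.69, 1.84, 1.23 and 0.92 per 100 patient-years.

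The planned table would look identical in all four cases, although the rate excluded differs fourfold.

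**Step 4: crude percentage against 24-month risk.** Let p be the true 24-month risk and F(t) = 1 − exp(ln(1 − p) × (t/24)^k). The expected crude percentage is the mean of F over the follow-up distribution. With k = 1 (constant hazard):

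| p | All followed 18 months | Follow-up uniform over 0–24 months |
|---|---|---|
| 10% | 7.6% | 5.1% |
| 40% | 31.8% | 21.7% |
| 70% | 59.5% | 41.9% |

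Timing of onset also matters. For p = 40% and uniform follow-up, the crude figure is 28.3% with early onset (k = 0.5) and 14.7% with late onset (k = 2). The gap from 2-year risk therefore cannot be corrected without knowing the exposure.

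**The case against.** **The information is already planned.** The dosing listing, the adverse-event onset times and the withdrawal study days give much of the picture subject by subject, and visit-level counts show roughly how many subjects remained. This stands: the missing element is the summary, not the data. But listings do not attach person-time to an adverse-event percentage.

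**Nothing promises a 2-year risk.** The study is descriptive, has no hypotheses, and treats for up to 2 years. This also stands, and it is why the point concerns interpretation rather than validity. Even so, a long-term safety objective invites the question of how long subjects were observed.

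**The integrated plan may cover exposure.** Protocol 9.0 puts the key analysis in a plan combining this study with TTP488-301. That plan is not available and may well handle person-time. The same section keeps the analysis of this study alone in the present protocol, so the stand-alone report still depends on these documents.

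**The display list is open.** SAP 9 is not exhaustive and SAP 5.5 allows further analyses. The claim is therefore that an exposure summary is not specified, not that it will be absent.

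**Stronger readings that do not hold.** A reader might infer from "There are no modifications from the Statistical Section of the Protocol" (SAP 1.9) and "This study has no plan for early stopping" (SAP 1.7) that exposure adjustment was considered and rejected. Neither supports this. SAP 1.9 is a general declaration and SAP 1.7 deals with monitoring and planned stopping; neither mentions exposure. A reader might also infer that the percentages are wrong, or that the comparison by prior arm is biased. They are correct for the follow-up observed, and nothing in the documents shows that follow-up differs between arms.

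**Conclusion.** The point holds as a gap in specification. The adverse-event part of the primary endpoint is planned only as counts or crude percentages of dosed subjects, and no summary of treatment duration, patient-years or exposure-adjusted incidence is specified. The textual finding is firm.

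The consequence is conditional. It rests on follow-up being truncated and unequal, which the early termination and staggered entry make likely but do not quantify. No size can be given for this study. The illustrations show only that one crude percentage, or one zero count, is compatible with rates differing about fourfold between 6 and 24 months of follow-up, given constant hazard in the first case. This is an inexpensive improvement to the reading of the primary objective and does not invalidate the planned tables.

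**What to change.** In SAP 5.3.1 and SAP 9:

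1. Add an extent-of-exposure table, with treatment-duration categories and total patient-years, by TTP488-301 arm and overall.
2. For any, serious, severe, related and discontinuation-leading TEAEs and for AESIs, report subjects with a first event per 100 patient-years at risk with a 95% confidence interval, beside the unchanged crude percentages.
3. State one at-risk window and apply it to both events and person-time. The definition in SAP 4.2.1 ("A treatment-emergent adverse event (TEAE) is an event that is observed or reported after administration of study medication") gives no end point of its own. The 45-day on-treatment rule in SAP 6.2 is a candidate, but it is not explicitly linked to TEAEs. No post-treatment visit is scheduled, so collection late in that window would be unscheduled. Events outside the chosen window can be listed separately.

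Cumulative incidence and rates by preferred term are optional.

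The cost is a few extra tables from dosing, adverse-event and disposition dates already collected. The main limitation is that comparing rates across different lengths of follow-up assumes a roughly constant hazard, which should be said in a footnote.

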Three interim analyses were planned during the study. The first interim analysis was conducted 6 months after approximately 50% of participants had been randomized. This analysis was conducted for the purposes of safety and for informing internal development decisions. The second interim analysis was conducted 12 months after all participants were randomized to assess futility, as well as for safety and to inform internal development decisions. A third interim analysis to inform internal development decisions was to be conducted when all continuing participants completed the Month 18 visit.

The first pre-specified interim safety analysis revealed an increased frequency of AEs (concentration related and reversible upon discontinuation of treatment), in particular falls and confusion, in the 20 mg/day group relative to the 5 mg/day and placebo groups. This was associated with a higher percentage of participants in the 20 mg/day group declining by ≥ 10 points on the ADAS-cog (relative to Baseline scores) at Months 3 and 6 (concentration related and stabilized/reversible upon discontinuation of treatment). There were no deleterious findings observed for either the 5-mg/day dose group or the placebo group. Participants randomized to the 20-mg/day dose discontinued study drug, received a safety evaluation, and were asked to consent to continue to be followed for safety clinical and laboratory assessments. Participants receiving 5 mg/day or placebo were re-consented and permitted to continue the study without modification.

Approximately 12 months after all participants were randomized, the second pre-specified interim analysis compared 5 mg/day and placebo for futility based on results of the completer population (i.e. those with available 18-month ADAS-cog data) Conditional power was computed based on assumed continuation of the observed trend.

While safety data raised no concerns, criterion for futility ($< 10\%$ conditional power to observe a significant difference between 5 mg/day and placebo at 18 months) was met (predicting a negative outcome) and treatment was discontinued. The third interim analysis was not performed as the study was terminated due to futility. Attempts to replicate the futility analysis, using a data set representative of that which would have been used for the futility analysis (constructed from the final data set), have been unsuccessful with conditional probabilities consistently computed as $> 20\%$.

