4.0 SUBJECT SELECTION

4.1 INCLUSION CRITERIA

Subject eligibility should be reviewed and documented by an appropriately qualified member of the Principal Investigator's (PI's) study team before participants are included in the study.

1. Successful completion of Study TTP488-301 through the Month 18 Visit without ongoing SAEs or history of serious adverse drug reactions during study TTP488-301.
2. Patients must enroll in the present study within 7 days of completion of study TTP488-301.
3. Evidence of a personally signed and dated informed consent document indicating that the subject (or a legally authorized representative) and caregiver/informant has been informed of all pertinent aspects of the study. Participants must be able to provide assent (where this is in accordance with local laws, regulations and ethics committee policy) and assent may be re-evaluated during the study at regular intervals.
4. Participants and caregiver/informants who are willing and able to comply with scheduled visits, treatment plan, laboratory tests, and other study procedures.
5. The subject must have a reliable caregiver/informant with regular contact (i.e., 10 hours a week as a combination of face-to-face visits and telephone contacts are acceptable) who will facilitate the subject's full participation in the study. Caregivers/informant must have sufficient subject interaction to be able to provide meaningful input into the rating scales administered in this study where caregiver/informant input is required, in particular the CDR and evidence of this should be documented in source documentation. Participants who reside in assisted living facilities are permitted provided that they meet caregiver/informant criteria.
6. Participants and caregiver/informants must be able to read, write, and speak the language in which psychometric tests are provided with visual and auditory acuity (corrected) sufficient to allow for accurate psychometric testing.

7. Subject must be able to ingest oral medications.

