1.4 Randomization

The open-label extension study was not randomized.

It is noted that TTP488-301 was randomized, and the randomization scheme for TTP488-301 is used to identify what will be called "treatment groups" in this SAP. The completers of TTP488-301 who are enrollees of TTP488-303 will be designated as

- Crossing over from placebo to azeliragon or
- Continuing on azeliragon.

Randomization in TTP488-301 had balanced allocation (1:1) between active and placebo. Dropouts were not allowed to be replaced.

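### TEAEs are tabulated only over the whole extension by former arm, so an early excess in subjects newly starting azeliragon would be diluted in the planned summary tables

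*SAP*

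**What the plan says.** SAP 1.4 divides enrollees into two groups: "Crossing over from placebo to azeliragon or" "Continuing on azeliragon". Only the first group begins the drug here. SAP 1.5 sets the planned duration: "Patients may receive azeliragon 5 mg/day for up to 2 years". The same section records that the study was stopped early.

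SAP 4.2.1 opens its definition with "A treatment-emergent adverse event (TEAE) is an event that is observed or reported after administration of study medication" and sets no time limit. Its variables are counts or proportions of subjects, for example "Proportions of subjects with TEAEs by System Organ Class and Preferred Term". SAP 5.3.1 asks for "Number (percent) of subjects reporting TEAE by treatment and overall in accordance with variables listed in Section 4.2.1". Severity and relatedness breakdowns are added there and in SAP 9.

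No sentence says outright that events are pooled over the whole extension. That follows because neither the SAP nor Protocol 9.3 plans an adverse event table by interval, by exposure or by time to first event. Elapsed time to onset is a column in the supportive listing of SAP 5.3.1 and nowhere else. By contrast, vital signs, laboratory values and ECG are summarised at each assessment (SAP 5.3.2, 5.3.3, 5.3.5), and efficacy scores at each time point by former arm (SAP 5.1.1).

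**The concern.** Adverse events come first among the primary endpoints (Protocol 2.2), yet they are the safety data summarised without a time dimension. The two display groups differ in one respect that matters for safety: one is new to azeliragon, while the other comes from 18 months of randomised azeliragon. An effect of starting the drug would appear as an early difference between groups that are otherwise observed concurrently and open-label.

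The documents give a reason to look early. Protocol 1.1.3 reports a mean half-life of 18 days in elderly participants. Five half-lives are 5 x 18 = 90 days, so new starters would approach steady state (1 - 0.5^5 = 97%) over about the first three months.

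A whole-period proportion adds later background events to both groups. In a population with progressing Alzheimer's disease, terms such as falls and confusion are likely to have an appreciable background. The overall column also mixes new starters with people who have already tolerated the drug.

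**Working it through.** **Inputs.** The plan has no event rate, power or sample size figure to reproduce. TTP488-301 planned 800 patients at 1:1 (SAP 1.4, 1.6), so the ceiling is about 400 per former arm; the number rolling over is not given. Everything else is assumed:
- background r = 1% per month for one event type (range 0.5-2%)
- excess e = 6 points in new starters, all within 6 months (range 4-8)
- n = 150 per former arm
- complete follow-up to time t

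**Formulas.**
- Continuing group: p0 = 1 - exp(-r t)
- New starters: p1 = 1 - (1 - p0)(1 - e), so p1 - p0 = e(1 - p0)
- SE = sqrt{[p0(1 - p0) + p1(1 - p1)]/n}; z = (p1 - p0)/SE

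Here z serves only as a yardstick for visibility, since the study allocates no alpha.

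**Base case.**

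| Period | p0 | p1 | Difference | Ratio | SE | z |
|---|---|---|---|---|---|---|
| 0-6 months | 5.8% | 11.5% | 5.7 points | 1.97 | 3.2 points | 1.75 |
| 0-12 months | 11.3% | 16.6% | 5.3 points | 1.47 | 4.0 points | 1.33 |
| 0-24 months | 21.3% | 26.1% | 4.7 points | 1.22 | 4.9 points | 0.96 |

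The loss in z is 1 - 1.33/1.75 = 24% at 12 months and 1 - 0.96/1.75 = 45% at 24 months. The difference itself shrinks only from 5.7 to 4.7 points. Most of the loss is added variance from background events.

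**Range.** Over r = 0.5, 1, 2% per month and e = 4, 6, 8 points, z falls by 17-29% at 12 months and 36-52% at 24 months. Because z is proportional to sqrt(n), these percentages do not depend on the assumed n.

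**Second model.** Put a 5-point excess entirely in months 0-3, with 200 per arm and two-sided 0.05 as a yardstick.
- Background 0.10 per year: 7.3% vs 2.5% at 3 months (ratio 2.98, power 62%), 14.0% vs 9.5% at 12 months (1.48, 29%), 22.2% vs 18.1% at 24 months (1.23, 17%).
- Rare term, 0.02 per year: the difference barely moves from 3 to 24 months (5.0 to 4.8 points), though power drops from 84% to 51%.
- Common term, 0.50 per year: the difference falls from 4.4 to 1.8 points.

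Both models show the same direction, with the heaviest dilution of the difference for common terms. Both place the whole excess inside the early window. If it were spread later, an early table would gain less.

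**The case against.** Five points count against a stronger claim.

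1. **Dose.** A reader might infer from Protocol 1.1.3 that early toxicity is expected here, since ADAS-cog worsening was seen "at Months 3 and 6 (concentration related and stabilized/reversible upon discontinuation of treatment". That was the 20 mg/day group, as were the excess falls and confusion. The same section reports nothing harmful at 5 mg/day, the dose given here, so it does not support the assumed 6-point excess. This stands in full.
2. **Other safeguards.** A reader might infer that such toxicity would go unnoticed altogether. The documents do not support that. Onset time is listed, qualified staff review the listings for signals (SAP 4.2), the IDMC reviews safety data (Protocol 9.6), and ADAS-cog is already summarised by visit and former arm. The gap is confined to the adverse event summary tables; listing review and the IDMC do not provide a between-group estimate there.
3. **Other evidence.** A reader might take this as the only comparison bearing on starting azeliragon. It is so only within the extension. TTP488-301 compared azeliragon with placebo under randomisation, and Protocol 9.0 leaves the key analysis to an integrated plan not available here. Protocol 9.0 still treats analysis of this study alone separately, so the table belongs in this SAP.
4. **Follow-up.** Early termination makes a full 24 months for everyone an extreme case. This stands, and the 12-month results are the milder alternative.
5. **Selection.** Protocol 4.1 requires "Successful completion of Study TTP488-301 through the Month 18 Visit without ongoing SAEs or history of serious adverse drug reactions during study TTP488-301". The rule applies to both arms, but only in the former azeliragon arm does it select people who tolerated azeliragon. An early difference could therefore reflect drug initiation or prior loss of intolerant subjects from the comparator. Interval tables cannot separate the two, so the contrast can only be descriptive.

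**Conclusion.** The point holds as a limitation of the planned summary tables. Whole-extension TEAE proportions by former arm would dilute an early excess among new starters. Under the stated assumptions z drops by 17-29% with 12 months' follow-up and 36-52% with 24, the latter being an upper bound given the early stop. The effect on the risk difference is small for rare terms and larger for common ones. Background rate, excess and group size are all assumptions. Even the 0-6 month table gives z of only 1.75 in the base case, so it would improve visibility without settling the question.

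The documents do not show that 5 mg/day causes early toxicity, and no commitment in the plan is breached. This is a low-cost improvement to the summary of the primary endpoint.

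**What to change.** Add to SAP 4.2.1 and 5.3.1 a descriptive TEAE table by onset period from first open-label dose: at least 0-6 and >6 months, with finer periods (0-3, >3-6, >6-12, >12 months) if numbers allow. Show it by former TTP488-301 arm, with subjects on treatment at the start of each period as denominator. Cover all, serious, severe and related TEAEs, falls, confusion, and the psychiatric and anxiety events of special interest in SAP 4.4.

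If a 0-6 month difference with 95% CI is shown, label it descriptive and note beneath the table that the continuing group is selected for tolerating azeliragon. State whether a later period counts any new onset or only a subject's first event. State also how partial onset dates are assigned to a period, since SAP 6.2 does not impute missing days. Keep the whole-period tables.

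Cost: SAP wording and a few tables from start dates already recorded (Protocol 8.6). Later periods will be sparse because of the early stop.
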